287 necessary after TKR for patients with osteoarthritis (OA) who could otherwise be discharged
288 directly home.

289 The main hypothesis to be tested by the proposed study is that TKR recipients who receive
290 inpatient rehabilitation in addition to participating in a home programme, compared to
291 patients who participate in a home programme only, will achieve a superior level of mobility
292 at 6 months post surgery. If superiority is shown, a cost-effectiveness analysis will be
293 undertaken.

294

295 Primary outcome

296 The primary outcome variable is walking distance at 6 months post surgery, measured using
297 the Six-Minute Walk Test (6MWT)^{17, 19}. Function measured by this test is a composite of
298 several factors targeted in rehabilitation programmes after TKA such as lower limb strength,
299 knee range of motion, and balance^{17, 18, 19, 20, 21}. The test is highly reproducible within the
300 individual²², is likely to be less susceptible to misinterpretation and less culturally sensitive

301 than patient-reported outcomes, and does not appear to suffer from the floor or ceiling effects
302 associated with many patient-reported outcomes²³ Together, these attributes mean the results
303 for our primary outcome should be readily translatable to any TKA cohort. Finally, a
304 functional outcome based on a physical test is a novel choice as a primary outcome in this
305 field with most TKA rehabilitation studies focusing on patient-reported outcomes^{12, 17, 18, 20, 24}.

306

307 2.2. SECONDARY OBJECTIVE

308 Secondary hypotheses to be tested relate to patient-reported knee pain and function, health-
309 related quality of life, and knee joint mobility. Superiority in these outcomes will be evident
310 at six months after surgery.

311

312 3. STUDY DESIGN*

313 3.1. DESIGN*

314 Two-arm, parallel randomised controlled trial with third observational group.

315 3.2. STUDY GROUPS

316 Two study groups (treatment arms).

317 1) HI – Hospital inpatient rehabilitation group

318 2) HO – Home-based rehabilitation group

319

320 Description of the interventions

321 (HI): Those allocated to the HI will be admitted to Braeside or Sutherland Hospital's
322 Rehabilitation Unit for 10 days. Informed by the private sector,²⁵ HI patients will receive
323 twice-daily supervised physiotherapy. Supervised therapy will comprise 1-1.5 hr of class-
324 based exercises and 1-1.5 hr of 1-to-1 therapy. After discharge, patients will be provided with

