325 a home programme (described below). Monitored Home Programme (HO) (standard care):
326 Approximately 2 weeks post-surgery, patients allocated to HO will attend 1 group-based
327 exercise session at Fairfield, Sutherland or Campbelltown Hospitals where the home
328 programme will be rehearsed and exercises individualised as per extant co-morbidities.
329 Patients will be encouraged to attend a 2nd class within the first 2-8 post-operative weeks to
330 encourage exercise progression and discuss any ongoing issues with the therapist. *Patients in*
331 *both groups will receive a booklet (see attached) detailing the home programme, and will be*
332 *permitted to contact the therapist by phone in this period for advice.* Any patient can be
333 reviewed at any time by the therapist within the first 8 weeks of surgery if there are any
334 concerns raised by either the patient or the therapist. All patients will be required to complete
335 a diary detailing programme adherence and healthcare utilisation.^{8,9}

336 Treating therapists will be required to complete a study proforma detailing therapy provided
337 and therapy attendance and any complications.

338 Therapy provided to those who do not consent to participate

339 Patients who do not consent to participate in the study will receive standard care, i.e. the HO
340 programme. Due to unforeseen circumstances, some may be discharged to inpatient
341 rehabilitation.

342

343 3.3. NUMBER OF PARTICIPANTS*

344 A minimum of 140 participants will be assigned to either the HI or HO groups with a
345 minimum of 70 in each group.

- 346 3.4. NUMBER OF CENTRES
347 - There are two recruitment centres and four treatment sites.
348 - Fairfield and Sutherland Hospitals are the recruiting sites. Fairfield, Sutherland
349 and Campbelltown Hospitals will oversee the monitored home programme.
350 - Braeside and Sutherland Hospitals will provide the inpatient rehabilitation.

351 3.5. DURATION
352 The study is expected to take approximately 48 months including 30 months for
353 recruitment, 12 months from enrolment of the last participant, and 6 months for
354 analysis.

355

356 4. PARTICIPANT SECTION

357 4.1. INCLUSION CRITERIA*

- 358 • Undergoing primary unilateral TKR at Fairfield or Sutherland Hospital
- 359 • Having a primary diagnosis of osteoarthritis
- 360 • Willingness to give written informed consent and willingness to participate
361 to and comply with the study.
- 362 • Age 40 years or over

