663 (The HIHO study): study protocol for a randomized controlled trial. *Trials* 2013; 14:432.

664 The study was registered prospectively in April 2012 on a clinical trials registry - U.S.
665 National Institutes of Health Clinical Trials Registry ref: NCT01583153.

666 **eMethods1. Statistical analysis plan**

667

668 **HIHO STATISTICAL ANALYTICAL PLAN (SAP) – JANUARY 2014**

669

670 **Background**

671 HIHO is a 2-armed parallel randomised controlled trial comparing 10 days on inpatient
672 rehabilitation followed by a hybrid home program (usual care) to a hybrid program alone in
673 people who have undergone a TKA. A third observational arm provides the opportunity to
674 assess the effect of preference on the measured outcomes as well as assess generalisability of
675 the randomised cohort.

676 Participants are randomly assigned via a central randomisation process to 1 of 2 arms. A
677 centralised randomisation service will be used for participant randomisation using a 1:1 ratio,
678 providing secure, coded randomisation via telephone. Group allocation, therefore, will be
679 concealed from all parties until the result of the randomisation is known. Participants will be
680 randomised to one of the two intervention groups using the method of minimisation stratified
681 for variables that affect the primary outcome (distance walked in the 6MWT - age (≤ 68 y,
682 >68 y), height (≤ 163 cm, >163 cm), and gender.

683 Participants are followed up by an assessor blind to treatment allocation at 10, 26 and 52
684 weeks.

685 Neither therapists or participants are blind to the intervention received.

686 Different therapists are involved in the delivery of the inpatient and home-based programs.

687 **Data management**

688 Data will be sent by blinded assessors to blinded data entry staff for collation and data entry,
689 with range checks for data values. All databases will be password protected and stored in
690 secure areas. Data will be checked for accuracy against the source documents by the study
691 coordinator after all participants are randomized and then when all participants have had their
692 final follow-up.

693 **Statistical plan**

694 **Outcome measures:** The primary outcome and most secondary outcomes will be measured
695 pre-operatively, at week 10 (the time when the home program formally ceases), and then at 6
696 and 12 months post-randomisation. Assessments will be performed by an observer blinded to

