727 weeks (knee flexion $> 100^\circ$ or $\leq 100^\circ$), a Generalised Estimating Equation model will be
728 used to test the treatment effect, with the adjustment of the covariates as above.

729 For the sensitivity analysis, we will also perform a per protocol analysis including only
730 patients who complied with the treatment protocol. Compliance for HI group will be defined
731 as attendance of a minimum of 7 days of inpatient rehabilitation, along with attendance at no
732 less than two outpatient sessions and no more than five. Compliance for the HO group will be
733 defined as attendance at no less than two outpatient sessions and no more than five.

734 There will be procedures put in place to minimise loss to follow-up, such as obtaining
735 multiple contact details at time of consent and reminders that assessments are due. The age,
736 gender and height of participants will be used as stratification variables in the randomisation
737 procedure via a minimisation algorithm. The mixed model analysis indicated above will
738 include these three variables as additional covariates to incorporate the possible within
739 treatment group correlation associated with by stratification [3].

740 For the analyses involving the observational arm, the change score in the primary outcome
741 will be compared between the observational group and those in the randomised home group
742 adjusting for other covariates. A lack of significant difference in scores between the two
743 groups will suggest there is no strong preference effect in this trial and we may not need to
744 include preference as a covariate in the RCT analyses. To be consistent with the two RCT
745 groups, we will aim for a minimum 64 participants in the observational group.

746 Cost-effectiveness analysis will be undertaken if the inpatient arm is shown to be superior.
747 Due to limited funding, we will no longer utilize data from the PBS or Medicare. Costs will
748 be based on standardized unit prices and based on patient diaries of expenses.

749

750

751 **References**

- 752 1. Sterne J, White I, Carlin J et al: Multiple imputation for missing data in epidemiological
753 and clinical research: potential and pitfalls. *BMJ* 2009; 338: b2393.
- 754 2. Donders R, van der Heijden G, Stijnen T, Moons K: Review: A gentle introduction to
755 imputation of missing values. *J Clin Epi* 2006 59: 1087e-1091.

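### A home-arm patient who attends the one session that protocol section 3.2 requires is excluded as non-compliant by the SAP's two-session per-protocol rule

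*Supplement*

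**What the plan says.** **Protocol version 5, section 3.2 (description of the interventions).** For HO: "Approximately 2 weeks post-surgery, patients allocated to HO will attend 1 group-based" exercise session, at which the home programme is rehearsed and tailored. Then: "Patients will be encouraged to attend a 2nd class within the first 2-8 post-operative weeks to" help patients progress and raise problems. Any further therapist review in the first 8 weeks depends on a concern raised by the patient or the therapist.

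For HI, section 3.2 specifies 10 inpatient days and then: "After discharge, patients will be provided with" a home programme, with a pointer to the HO description that follows.

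**SAP, Background.** The comparison is described as inpatient "rehabilitation followed by a hybrid home program (usual care) to a hybrid program alone in" knee replacement patients, so both arms are given the same kind of home programme.

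**SAP, Analyses subsets.** "For the sensitivity analysis, we will also perform a per protocol analysis including only" those "patients who complied with the treatment protocol. Compliance for HI group will be defined" as at least 7 inpatient days plus two to five outpatient sessions. For HO, compliance is "defined as attendance at no less than two outpatient sessions and no more than five".

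Under the same heading, the SAP states that the main analysis is by intention to treat and includes everyone randomised, whatever their compliance.

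**The concern.** The SAP states what its per-protocol set is meant to be, namely patients who followed the treatment protocol. It then gives a rule that does not produce that set for HO. The second class is optional in section 3.2 and compulsory in the SAP.

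What is at stake is the meaning of the only analysis the SAP labels as a sensitivity analysis. It is presented as asking whether the result holds among patients who followed the protocol. As defined, it asks, for HO, whether the result holds among patients who also took up an optional class or had another outpatient session. Any per-protocol set selects on behaviour after randomisation. This one also selects on a choice that section 3.2 leaves open, and not only on departures from what it requires.

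**Working it through.** No estimate is needed; the check compares two rules.

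**Inputs**
- Sessions required of HO: 1 (protocol 3.2).
- Status of the second HO session: encouraged, in weeks 2 to 8 (protocol 3.2).
- Other therapist contact: optional and concern-driven (protocol 3.2).
- HO compliance range: 2 to 5 outpatient sessions (SAP, Analyses subsets).
- HI compliance: at least 7 inpatient days plus 2 to 5 outpatient sessions (same place).

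**Step 1. The two rules applied to an HO patient**

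| Outpatient sessions attended | Meets the 3.2 attendance requirement? | In the SAP per-protocol set? |
|---|---|---|
| 0 | No | No |
| 1 | Yes | No |
| 2 to 5 | Yes | Yes |
| 6 or more | Yes (3.2 states no ceiling) | No |

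The one-session row is the contradiction. The last row is not disputed: section 1.2 presents the home programme as using few resources, and a ceiling protects that contrast.

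**Step 2. Could the term outpatient session reconcile them?** The SAP does not define it, so it might include individual reviews as well as classes. That does not help. Section 3.2 allows reviews only when a concern arises, so an uneventful patient with the one required class still has a count of 1 and is excluded.

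**Step 3. Does any other text make the second class mandatory, or explain the threshold of two?** None was found in the protocol or the SAP. Both are dated January 2014, so this is not a difference between versions.

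**Step 4. Does the same follow for HI?** The one-session wording names HO patients only. For HI it would have to come through the pointer to the home programme, and the SAP Background supports that reading. Against it, the class falls at about 2 weeks. Section 5.6 has randomisation 3 to 4 days after surgery, and 10 inpatient days from then run to about day 3 + 10 = 13 or 4 + 10 = 14. The HO timing therefore does not transfer cleanly. The HI requirement is an inference.

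**Step 5. Size.** The gap in the rule is 2 − 1 = 1 session. The number of patients in the one-session row is not given and cannot be derived.

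**Background check.** The planned sample size does not depend on this rule, and it reproduces. With 60 m, SD 120 m, two-sided 5% and 80% power, n = 2 × (1.96 + 0.84)² × (120/60)² ≈ 63 per arm, and 63/0.9 = 70.

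**The case against.** The strongest defence is that the SAP prespecifies a dose window and the complaint is only about its label. The second class has a purpose and a time window in section 3.2, so two sessions could be seen as the intended dose. The SAP also departs from section 3.2 elsewhere: it accepts 7 inpatient days where the protocol gives 10, and it adds a ceiling of five. Using one outpatient window in both arms keeps that component similar.

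Part of this stands. Two sessions is a reasonable threshold for an attendance analysis, and prespecifying it is good practice. But the SAP calls the set patients who complied with the treatment protocol. Accepting 7 of 10 days is more lenient than the protocol, so it excludes nobody who did what was asked. Requiring two sessions is stricter than the protocol, so it does exclude such patients. The dose-window defence does not answer that.

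The objection that the HI half is inferred also stands, and the point is limited accordingly.

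A reader might infer three stronger things that the documents do not support:
- **A large loss of patients or precision.** Any such figure would need an assumed share stopping at one session, and it would measure precision, not selection.
- **A bias of known direction or size.** Nothing in the documents allows one to be derived.
- **That concern-driven reviews should be exempt from the limit of five.** The SAP is silent on this. An exemption could admit patients with many individual reviews, which would weaken the low-resource contrast.

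**Conclusion.** The point holds for HO as a matter of text: section 3.2 requires one session, the SAP's compliance rule requires two, and an HO patient with exactly one is wrongly classed as non-compliant. For HI it holds only on the assumption that the pointer to the home programme carries the one-session requirement.

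The consequence is minor. It touches the per-protocol sensitivity analysis alone; the intention-to-treat primary analysis and the sample size are unaffected. A mislabelled sensitivity analysis is still worth correcting, because it is the only one the SAP names and the correction is cheap.

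**What to change.** Amend the SAP before unblinding. Section 3.2 can stay as it is.

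1. Set the per-protocol lower bound at one outpatient session for HO. Apply the same bound to HI once the SAP confirms that the home programme's one-session requirement applies to that arm.
2. Keep the minimum of 7 inpatient days for HI and the upper limit of five sessions.
3. Report patients with two or more sessions, within the same upper limit, as a separate analysis labelled *higher attendance*. This keeps the comparison the SAP now specifies, under an accurate name.
4. Report the number excluded from each set, by arm, with reasons.

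**Cost.** SAP wording and one extra sensitivity analysis. The per-protocol set will have a somewhat lower average outpatient dose. No new data are needed: therapists already record attendance on the study proforma (section 3.2), and the study obtains it directly from them (section 5.2).

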Evidence in support of inpatient rehabilitation after TKR Our own systematic search of key electronic healthcare databases (May 30, 2011) revealed that there was no high-level evidence to support the provision of inpatient rehabilitation after TKR. Specifically, no randomised trial has compared inpatient rehabilitation to any out-patient mode or a monitored or unmonitored home programme. Several studies undertaken in the US have concluded that inpatient rehabilitation is not superior to domiciliary rehabilitation (hospital services provided at home).^{11,12} A non-randomised pilot study in Germany concluded that inpatient rehabilitation was not more cost-effective compared to out-patient rehabilitation.¹³ Longitudinal data from an Australian cohort⁹ observed that patient-reported outcomes were similar whether or not TKR patients were discharged to inpatient rehabilitation. The authors concluded, therefore, that randomised trials were required to explore who benefits most - such as the older or more infirm patients - from inpatient rehabilitation.

Evidence in support of non-inpatient modes of rehabilitation A recent systematic review concluded that there was insufficient evidence to support any specific type or mode of outpatient rehabilitation over any other outpatient mode or even a home programme.¹⁴ This included the use of hydrotherapy, 1-to-1 or group-based therapy, and even different exercise types such as those targeting function versus isolated muscle groups. Notably, most of the studies to date have been small ($n \leq 160$) and none have simultaneously compared group-based, 1-to-1 and home-based programmes. Our own recently completed, comparatively large RCT ($n = 249$) provides strong evidence that 1-to-1 centre-based therapy is not superior to a group-based programme or a monitored home programme at 10 and 52 weeks post surgery.¹⁵ The similar recovery patterns observed was despite the fact that access to centre-based interventions for the outpatient groups was optimised through the use of transport and parking concessions. Thus, lack of access or poor attendance did not explain a lack of superiority of the 1-to-1 mode.

254 1.2. RATIONALE FOR PERFORMING THE STUDY*

255 In Australia, inpatient rehabilitation is a costly and commonly utilised treatment option after
256 TKR surgery, particularly in the private sector. A 12-day inpatient stay in a private facility

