List	Enrolment	Week 10	Week 26	Week 52
------	-----------	---------	---------	---------

Interventions	Visit			(Final)
Informed Consent	✓			
Inclusion / Exclusion criteria	✓			
Nomination of preferred Rx method	✓	✓		
Obtain demographic and anthropometric data	✓	Weight only	Weight only	Weight only
Complete KOOS, EQ5D, Oxford surveys	✓	✓	✓	✓
Six minute walk test (gait speed and distance)	✓	✓	✓	✓
15 metre walk test	✓	✓	✓	✓
SF12 or EQ-5D	✓	✓	✓	✓
Patient-reported adverse event		✓	✓	✓
Postacute healthcare utilisation costs		✓	✓	✓

429

430

431

432

433

434

435

436

437

438

439

440

Each test or survey will be completed according to standardised protocols, and conducted by an assessor blinded to the treatment allocation. The assessments will take place at Fairfield Hospital (Whitlam Joint Replacement Centre or the Pre-Admission Clinic), Sutherland Hospital (Preadmission Clinic) or Campbelltown Hospital (Physiotherapy Department). Occasionally it may be necessary for a follow-up assessment to be conducted at a participant's home, in the event that this is deemed the only way that an outcome measure may be collected for a participant, for example when participants are unable to come to the designated hospital for follow-up due to transportation or other issues. Patients will be given diaries to complete their record of healthcare utilisation after discharge from acute care or from inpatient rehabilitation. Acute care costs will be ignored as they will be assumed to be the same for all patients. Length of stay will not be dictated by the study as

441 the normal criteria for discharge from acute care will apply independent of which study arm
442 the patient is in. Costs of rehabilitation will commence from either discharge to inpatient
443 rehabilitation or discharge home. The inpatient rehabilitation costs will be estimated from
444 known costs of TKR inpatient episodes in a private facility. Other healthcare costs will be
445 derived from the standard Medicare Schedule and Pharmaceutical Benefits Schedule for the
446 study time period.

447

448 Study endpoints

449 The data collection phase of the study will end when the last randomised patient has their 12-
450 month assessment. The entire study will end after the analysis involving all participants is
451 complete.

452

453 5.3. STUDY PROCEDURE RISKS*

454 We do not anticipate that the patient is exposed to any further risk than they would

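### Healthcare-use diaries start later in the inpatient arm than the costing does, and the stay is covered by an external price with no itemised record of extra use

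*Supplement*

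**What the plan says.** Protocol section 5.2 (Investigation plan, text below the assessment table) sets three rules for costs.

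- Start of costing: "Costs of rehabilitation will commence from either discharge to inpatient" rehabilitation or discharge home. In both arms that is the day the patient leaves acute care, whose own costs are left out as equal.
- Start of recording: "Patients will be given diaries to complete their record of healthcare utilisation after discharge from acute care or from inpatient rehabilitation". For a home patient this is acute discharge. For an inpatient-arm patient it is the end of the rehabilitation stay.
- Price of the stay: estimated from "known costs of TKR inpatient episodes in a private facility".

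Section 3.2 plans the inpatient-arm stay as "Rehabilitation Unit for 10 days". It also requires a diary from every patient, without a start date, and a therapist proforma on therapy, attendance and complications. Section 6.1 adds adverse-event monitoring through the physiotherapists and at follow-up visits.

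The only private-facility price in the documents is in section 1.2: "A 12-day inpatient stay in a private facility" is put at roughly $7000.

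The SAP (January 2014) drops PBS and Medicare data and says that costs will "be based on standardized unit prices and based on patient diaries of expenses". It does not mention the diary start, the private episode price or a source for bed-days. The cost-effectiveness analysis is to be done only if the inpatient arm is superior (protocol sections 1.2 and 2.1, and the SAP).

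**The concern.** A cost comparison between arms is easiest to defend when both arms are measured over the same period by the same method. Here the period is the same and the method is not. In the first days after acute care, the home arm contributes patient-reported use and the inpatient arm contributes an external price.

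A price for a routine episode does not vary with what happened to the individual. If an inpatient-arm patient is transferred back to acute care or sent for a non-routine investigation during the stay, the plan names no place where that use is itemised for costing. The same event in a home patient on the same day falls within the diary. Because the SAP gives up the administrative sources, the diary carries more of the weight, and its timing matters more.

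At stake is the cost side of a contingent secondary analysis. Section 1.2 nevertheless makes cost-effectiveness part of the working hypothesis and notes its interest to insurers and governments. The diaries also have to be collected before anyone knows whether the analysis will be run.

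**Working it through.** The plan states no figure on this point that could be reproduced. The check sets the rules side by side, then sizes the gap and the pricing question.

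**Rules by arm**

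| | Home arm | Inpatient arm |
|---|---|---|
| Costing starts | Acute discharge | Acute discharge |
| Diary starts | Acute discharge | Discharge from inpatient rehabilitation |
| Source for the first 10 days or so | Diary | Private-facility episode cost |
| Complications in those days | Proforma, adverse-event monitoring, diary | Proforma, adverse-event monitoring |

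**Size of the diary gap**

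Inputs: a planned stay of 10 days (section 3.2) and assessments at weeks 10, 26 and 52 after surgery (section 5.2). The day of acute discharge is not given; days 4 to 7 are assumed.

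Share of the window without a diary = 10 / (7 × weeks − day of acute discharge):

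- Week 10: 10/(70 − 4) = 10/66 = 15.2%, to 10/(70 − 7) = 10/63 = 15.9%.
- Week 26: 10/(182 − 4) = 10/178 = 5.6%, to 10/(182 − 7) = 10/175 = 5.7%.
- Week 52: 10/(364 − 4) = 10/360 = 2.8%, to 10/(364 − 7) = 10/357 = 2.8%.

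The SAP counts an inpatient-arm patient as compliant, on this component, with "as attendance of a minimum of 7 days of inpatient rehabilitation", so some gaps may be shorter. At 7 days the share to week 10 is 7/66 = 10.6% to 7/63 = 11.1%. In the home arm the share is zero throughout.

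These are shares of time without a diary. They are not shares of cost left out, because the inpatient days are priced.

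**What the price could do, under one assumption**

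Inputs: $7000 for 12 days (section 1.2) and a 10-day stay (section 3.2).

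- Per day: 7000/12 = $583.
- Pro rata for 10 days: 583.33 × 10 = $5833.
- Excess if the full 12-day price were charged for 10 days: 7000 − 5833 = $1167, and 1167/5833 = 20%.

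This excess arises only if that particular price is used and is not scaled to the length of stay. The documents say neither.

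**The case against.** The strongest reply is that this is an ordinary division of labour: an episode price covers the admission, the diary covers what follows, and nothing is counted twice. Section 1.2 makes the private-sector model a deliberate choice. That stands. A reader might infer that about 10 days of inpatient-arm costs are missing; they are not.

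A reader might also infer a fixed overcharge of 20%. The documents do not support that. The $7000 figure is background in the rationale and is nowhere named as the costing input. Section 5.2 speaks only of estimating from known costs, and the SAP's standardised unit prices could well be per day.

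Nor is it right that events during the stay go unseen. The proforma and adverse-event monitoring cover both arms, and the section 5.2 table schedules collection of post-acute utilisation costs at weeks 10, 26 and 52 without distinction by arm. This gives complications a route into the trial data. It does not give an itemised record of the resources used, and no document says that the visit-based collection reaches back over the inpatient stay.

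Two further inferences fail. One is that intervals around the cost difference would be too narrow. That presumes one fixed price for every patient, which is not specified. The other is that the effects could never be disentangled later. The 7-day compliance rule requires inpatient days to be known per patient, and admission records should show transfers.

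Finally, the analysis is conditional on superiority. That lowers the priority, but it does not make the ascertainment comparable.

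**Conclusion.** The point holds as a difference in how costs are ascertained, not as a demonstrated bias. Costing starts at acute discharge in both arms, while diaries start at acute discharge in one and after a planned 10-day stay in the other. The stay is priced externally, and use outside routine rehabilitation during it has no itemised cost record.

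The gap is early: about 15 to 16% of the time to week 10 and about 3% to week 52, assuming a 10-day stay and acute discharge on days 4 to 7. The net sign is unknown: unrecorded extra use would understate the inpatient arm's cost, and an unscaled 12-day price, if it were used, would overstate it.

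The 6MWT primary outcome is untouched, and the cost analysis may never be run. This is a low-priority improvement, worth making because it is cheap and because diary entries not made at the time are hard to reconstruct.

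**What to change.** - **Protocol section 5.2:** issue the same diary to both arms at discharge from acute care, with days in inpatient rehabilitation marked as such.
- **SAP costing paragraph, unit cost:** cost inpatient rehabilitation as each patient's actual bed-days, taken from the hospital record, times a stated per-day private-facility unit price. Apply this in either arm, so that a home-arm patient who is admitted to rehabilitation is costed in the same way.
- **SAP costing paragraph, extra use:** add separately any transfer, readmission or non-routine investigation during the stay, and say what the per-day price already includes so that nothing is counted twice.
- **Patients already enrolled:** take bed-days and transfers from the admission record.

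The cost is about 10 more diary days for each inpatient-arm patient, minor extraction from records that the sites already hold, and one SAP paragraph. Treatment and the clinical outcomes are not affected.
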